
Methodology (Cont):
 
Part 1
 
During Part 1 of the study, approximately 100 subjects (25 per treatment arm) will be randomized to receive a single dose injection femoral nerve block with either one of three doses of liposome bupivacaine (67, 133, or 266 mg) or placebo in 20 mL under ultrasound guidance. Preservative-free normal saline will be added to the 67 mg and 133 mg doses of study drug to achieve a volume of 20 mL.
 
After all subjects have completed the 72-hour assessments in Part 1, an analysis will be conducted in order to select a single therapeutic dose from the three liposome bupivacaine dose levels tested. An unblinded dose selection committee will review at least the results from the following assessments conducted during Part 1: (1) the area under the curve (AUC) of the numeric rating scale (NRS) at rest (NRS-R) pain intensity scores through 72 hours; (2) total postsurgical opioid consumption; (3) the time to first opioid rescue; and (4) safety data. Based on a clinical evaluation of the data, the committee will determine the apparent efficacy and safety of each of the three liposome bupivacaine dose levels tested and will recommend a dose level for Part 2 of the study. Statistical significance will not be required in order to recommend a dose level for Part 2. The unblinded dose selection committee also will recommend whether the sample size for Part 2 should be increased.
 
Part 2
 
In Part 2 of the study, approximately 180 subjects (randomized 1:1, resulting in approximately 90 liposome bupivacaine subjects and 90 placebo subjects) will receive a single dose injection femoral nerve block with the selected dose level of liposome bupivacaine (i.e., 67, 133, or 266 mg) or placebo in 20 mL under ultrasound guidance.
 
Postsurgical Rescue Medication
 
Subjects should only receive rescue medication upon request for pain control, as needed.
 
The first rescue medication will be intravenous (IV) hydromorphone 0.5 mg, which will be administered once via bolus only. At this time, the PCA should be loaded with opioid (morphine or hydromorphone only).
 
The second rescue medication will be an on-demand PCA-administered opioid (morphine or hydromorphone). The PCA pump will be programmed to deliver either on-demand morphine or on-demand hydromorphone boluses at a dose and lockout interval in accordance with the site's standard practice. A continuous infusion (background or basal rate) of morphine or hydromorphone is not permitted. If the subject's pain is excessive or pain control is inadequate, then the bolus dose may be adjusted according to local hospital practices; however, adding a basal rate is prohibited. Once a subject is tolerating oral (PO) medication, PO immediate-release oxycodone may be administered (but not more than 10 mg every 4 hours).
 
If a subject's pain is inadequately controlled by opioids, a third rescue medication consisting of conventional bupivacaine HCl at a concentration of 0.125% (1.25 mg/mL) at a rate of 8 mL per hour for up to 12 hours may be administered via the previously placed femoral nerve catheter.
 
Subjects who do not achieve adequate pain relief with this regimen will be withdrawn from the study and followed for AEs only. No other analgesic agents, including non-steroidal anti-inflammatory agents (NSAIDs), are allowed during the 72-hour observation period or until the subject is withdrawn from the study, whichever is sooner.
		

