9. STUDY DESIGN AND PLAN

9.1. Study Design

This is a Phase 2/3, multicenter, randomized, double-blind, parallel-group, placebo-controlled, dose-ranging study in subjects undergoing primary unilateral total knee arthroplasty (TKA) under general or spinal anesthesia. Note: Bupivacaine cannot be used as the spinal anesthetic.

On Day 1, eligible subjects will be randomized to receive a single dose of study drug administered within 2 hours prior to the surgical procedure as a femoral nerve block. Study drug administration will be performed in a blinded manner (see [Section 11.5.1](#)). At the conclusion of the block, a femoral nerve catheter is to be left in place and hep-locked (see “[Postsurgical Rescue Medication](#)” below). Additionally, a patient-controlled analgesia (PCA) pump will be established prior to the completion of the surgery. *The PCA pump will not be loaded at this time.* The use of fentanyl will be permitted during surgery. However, intraoperative administration of morphine or any other analgesics (including intrathecal opioids), local anesthetics, or anti-inflammatory agents is prohibited, unless needed to treat an AE.

All subjects will be required to remain in the study site for a minimum of 72 hours after the end of surgery for postsurgical assessments. The study staff will ensure adequate safety precautions are in place in order to prevent falls (e.g., use of support devices during ambulation, such as a knee immobilizer and walker/crutches) as needed.

Part 1

During Part 1 of the study, approximately 100 subjects (25 per treatment arm) will be randomized to receive a single dose injection femoral nerve block with either one of three doses of liposome bupivacaine (67, 133, or 266 mg) or placebo in 20 mL under ultrasound guidance. Preservative-free normal saline will be added to the 67 mg and 133 mg doses of study drug to achieve a volume of 20 mL.

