Third Rescue Medication (Conventional Bupivacaine HCl)

If a subject's pain is inadequately controlled by opioids, a third rescue, a femoral nerve block, consisting of conventional bupivacaine HCl at a concentration of 0.125% (1.25 mg/mL) at a rate of 8 mL per hour for up to 12 hours may be administered via the previously placed femoral nerve catheter.

Subjects who do not receive adequate pain control with this regimen are to be withdrawn from the study and followed for AEs only. No other analgesic agents, including non-steroidal anti-inflammatory agents (NSAIDs), are allowed during the 72-hour observation period.

Postsurgical Assessments

Postsurgical assessments will include pain intensity scores using the 0-10 point NRS-R and NRS with activity (NRS-A) (where the prescribed activity is active knee flexion up to 45 degrees) (see [Appendix 1](#)); use of supplemental opioid pain medication; neurological assessment (see [Appendix 2](#)); cardiac assessment [i.e., ECG recordings]; sensory function assessment [i.e., cold test]; motor function assessment [i.e., 20-meter walk test]; vital signs; overall benefit of analgesia score (OBAS) questionnaire (see [Appendix 3](#)); subject satisfaction with postsurgical pain control (see [Appendix 4](#)); physician satisfaction with return of sensory/motor function (see [Appendix 5](#)); and an opioid-related AE questionnaire during Part 1 only (see [Appendix 6](#)). Adverse events will be recorded through Day 30. If a cardiac or neurological event occurs during Part 1 or Part 2 of the study that the Investigator believes may be associated with high levels of systemic bupivacaine, an unscheduled PK blood sample should be collected at the time that the event is noted.

Safety and efficacy assessments will be conducted at pre-specified time points *after the end of surgery* (defined as the time of last suture/staple). A follow-up visit will be scheduled for all subjects on Day 30.

Pharmacokinetic Assessments (Part 1 only)

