10.3. Removal of Subjects from Therapy or Assessment

Every reasonable effort should be made to maintain subject compliance and participation in the study. Reasons for discontinuation of any subject from the study will be recorded.

Subjects who withdraw from the study postsurgically should be followed for AEs. All AEs that occur through Day 30 after surgery must be recorded. If a subject who withdraws from the study has an ongoing AE, every effort must be made to follow such events until satisfactory resolution is obtained, or further follow-up is otherwise no longer warranted.

Safety assessments performed during the early termination visit should include the neurological examination, cold test, 20-meter walk test, and collection of a blood sample for PK analysis, if possible.

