11.6.2. Permitted and Restricted Therapy or Medications During Surgery

Permitted

- Short and ultra-short acting opioids (e.g., fentanyl) will be allowed during surgery.

Restricted

- Bupivacaine cannot be used as the spinal anesthetic.
- No agents are to be admixed with liposome bupivacaine (e.g., epinephrine, dexamethasone, and clonidine).

- Lidocaine and other local anesthetics will not be permitted to be locally administered during the surgery because they are known to interact with liposome bupivacaine resulting in the displacement of bupivacaine and elevated plasma levels.
- Intrathecal opioids.
- The use of opioids other than fentanyl (e.g., morphine, hydromorphone HCl), acetaminophen, ketorolac, or other NSAIDs will not be permitted intraoperatively except for emergency use to treat an AE.
- Entereg (alvimopan) use is prohibited.
- Prophylactic antiemetics or planned postsurgical antiemetics given without regard to the subject's emesis needs is prohibited.

11.6.3. Permitted and Restricted Therapy or Medications After Surgery through 72 Hours After Surgery

Permitted

- Rescue medication use is permitted as described in [Section 11](#).

Restricted

- No other analgesics are permitted within 72 hours after surgery.
- Entereg (alvimopan) use is prohibited.
- Prophylactic antiemetics or planned postsurgical antiemetics given without regard to the subject's emesis needs.
- Dexmedetomidine HCl (Precedex) use is prohibited.

For study purposes, it is important to standardize pain management modalities during the first 72 hours following study drug administration. Therefore, the study staff must adhere closely to the treatment options and requirements noted in the protocol. After 72 hours, the analgesic regimen may be adjusted for each subject individually, as deemed appropriate by the physician responsible for the postsurgical care.

All concomitant medication will be recorded through 72 hours after the end of surgery or until the subject is withdrawn from the study, whichever is sooner.

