13.1. Instructions for Conducting Procedures and Measures

With the exception of the PK assessments (which will be conducted after the beginning of study drug administration), all assessments conducted after baseline will be timed from the end of surgery. Day 1 is defined as the day on which study drug is administered. The beginning of surgery is defined as the time of the first incision. The end of surgery is defined as the time of the last suture/staple. Postsurgical is defined as after the end of surgery.

Subjects will be hospitalized for at least 72 hours after surgery; therefore, postsurgical analgesia and collection of study data through the primary endpoint will take place under the supervision of study staff.

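### Subjects withdrawn because rescue failed have no pain score listed at or after withdrawal; their later pain and opioid use are imputed, and no sensitivity analysis tests this

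*Protocol*

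**What the plan says.** **Withdrawal rule.** Under the protocol Synopsis (Postsurgical Rescue Medication), subjects without adequate relief on the rescue regimen "will be withdrawn from the study and followed for AEs only". Section 9.1 repeats it: they "are to be withdrawn from the study and followed for AEs only".

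**What is collected at withdrawal.** Section 10.3 says the early-termination assessments "should include the neurological examination, cold test, 20-meter walk test, and collection of a blood sample for PK analysis, if possible". Section 13.6 gives the same set. Neither lists an NRS score.

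**Medication recording.** In section 11.6.3, "concomitant medication will be recorded through 72 hours after the end of surgery or until the subject is withdrawn from the study", whichever comes first; section 11.6.1 has the same limit. Section 13.5, however, asks for the date, time and amount of all rescue medication through 72 hours with no withdrawal limit, and section 15.6.3.2 counts all opioids given through 72 hours.

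**Hospital stay.** Section 9.1: "All subjects will be required to remain in the study site for a minimum of 72 hours after the end of surgery". Section 13.1: "Subjects will be hospitalized for at least 72 hours after surgery".

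**Analysis.** The efficacy set (Protocol 15.4, SAP 6) takes in every treated subject who has the planned surgery, so withdrawn subjects remain in it. SAP 7.1.2 first replaces scores recorded inside a rescue window by the worst pre-rescue score (wWOCF), then fills scores missing after the last observation by LOCF. SAP 7.1.3 projects opioid use after discontinuation from the average rate before it, and SAP 7.6.2.2 applies this to the first secondary endpoint. The one sensitivity analysis of the primary endpoint (SAP 7.6.2.1) excludes subjects with PCA interval data.

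**The concern.** Failure of the rescue regimen is itself an efficacy outcome, yet the plan makes it a reason to stop scheduled efficacy data. The resulting gap falls on subjects with poor pain control, and in a placebo-controlled analgesic trial it may well be unequal between arms. It affects the primary endpoint and the first secondary endpoint. The latter also gates the test of time to first opioid rescue (SAP 7.1.4).

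Scheduled scores are 12 hours apart after hour 12. With no score at withdrawal, the last observation can be about 12 hours old and can predate the failure. The SAP disposition tables carry lack of efficacy as a termination reason, so such cases are expected. No planned analysis shows how far the result depends on the values filled in for them.

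**Working it through.** **1. The plan's own figures.**

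Power (Protocol 15.3, SAP 8): difference 61, SD 104, 90 per arm, two-sided 0.05. The standard error is 104 × √(2/90) = 15.5, and 61/15.5 = 3.93. Power is Φ(3.93 − 1.96) = 97.6% by the normal approximation and 97.5% by the noncentral t with 178 degrees of freedom. The stated figure of more than 97% reproduces. It makes no allowance for withdrawal or imputation.

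Projection example (SAP 7.1.3): discontinuation at 6 hours, total through 24 hours = A + (A/6) × (24 − 6) = 4A, where A is the observed amount. In general the multiplier to 72 hours is 72/T for withdrawal at hour T.

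**2. Share imputed per withdrawn subject.** The share of the 72 hours is (72 − T)/72. For the opioid total it is also the share of the amount. For pain it is a share of hours, not of AUC.

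| Withdrawal hour T | Share imputed | Opioid multiplier 72/T |
|---|---|---|
| 6 | 92% | 12 |
| 12 | 83% | 6 |
| 24 | 67% | 3 |
| 36 | 50% | 2 |
| 48 | 33% | 1.5 |
| 60 | 17% | 1.2 |

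For pain, imputation runs from the last score rather than from T. A subject withdrawn just before the 36-hour score has a last score at 24 hours, and so about 48 hours filled in.

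**3. Possible effect on the primary comparison.** The documents give no withdrawal rate, timing or imbalance, so everything here is assumed. Let w_P and w_A be the shares withdrawn on placebo and active, and e the carried-forward score minus the actual score. Then

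shift in mean AUC difference = (w_P − w_A) × (72 − T) × e.

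| Net placebo excess | T | e | Shift (NRS-hours) | % of 61 |
|---|---|---|---|---|
| 5 points | 48 h | 1 | 0.05 × 24 × 1 = 1.2 | 2% |
| 10 points | 24 h | 1 | 0.10 × 48 × 1 = 4.8 | 8% |
| 10 points | 24 h | 3 | 0.10 × 48 × 3 = 14.4 | 24% |
| 15 points | 12 h | 3 | 0.15 × 60 × 3 = 27 | 44% |

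With e positive, excess placebo withdrawal inflates the treatment difference; with e negative it shrinks it by the same amount. In the third row an apparent 61 would correspond to 61 − 14.4 = 46.6, a difference for which 90 per arm gives about 85% power.

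**4. Opioid endpoint.** It is analysed on the log scale. With a net placebo excess of 10 points, the geometric mean ratio (active/placebo) is multiplied by exp(−0.10 × ln r), where r is projected over actual total use. This gives 0.93 for r = 2, 0.90 for r = 3 and 1.07 for r = 0.5.

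**5. Recording rules side by side.** Synopsis and 9.1: AEs only after withdrawal. 11.6.1 and 11.6.3: concomitant medication until withdrawal. 13.5: all rescue medication through 72 hours. 15.6.3.2: all opioids through 72 hours. SAP 7.1.3: projection after withdrawal. A site cannot follow all of these. Even on its widest reading, 13.5 names only the regimen's own drugs, so other analgesics given after withdrawal could be missed. Separately, 9.1 bars other analgesics for the whole 72 hours, whereas the Synopsis and 11.1 end that bar at withdrawal; these passages must also be reconciled.

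**The case against.** The strongest reply is that the primary analysis already deals with these subjects conservatively. Anyone who fails the whole regimen will normally have received the bupivacaine infusion. Scores from its start until 12 hours after its end are replaced by the worst pre-rescue score, which includes the score at first rescue request, and higher observed scores are kept. Because this step is listed before LOCF, the carried score may already have been raised. This stands. A reader might infer that the primary result rests on a stale, low score carried forward, but the SAP does not support that as the general case. It does leave an error in the other direction open: a raised score carried to 72 hours can overstate pain once other analgesics are given.

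Three further inferences go beyond the documents:

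- *That withdrawn subjects are certainly in hospital for 72 hours.* The stay is stated for all subjects in order to carry out assessments; no section says that a withdrawn subject must stay. Availability for scoring is a reasonable inference only.
- *That no analgesic use is recorded after withdrawal.* Sections 13.5 and 15.6.3.2 point the other way, and section 11.6.1 keeps medication given for AEs through Day 30. The rules conflict; they do not set a clean stop.
- *That the comparison cannot be checked with observed data.* Scores before withdrawal are observed, NRS-R by time point and shorter AUCs are analysed, Listing 16.5.1.1 shows actual beside imputed scores, and receipt of all three rescues is compared between arms. Only the part after withdrawal is unobserved.

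It is also fair that scores after withdrawal reflect analgesia outside the protocol, so their value lies mainly in a sensitivity analysis.

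**Conclusion.** The point holds as a correctable weakness that the sponsor should address. Efficacy data stop on an outcome-dependent trigger, no pain score is listed at that moment, the recording rules conflict, and no sensitivity analysis covers the imputed stretch. Per subject the size is certain: withdrawal at 24 hours leaves 67% of the interval imputed and triples observed opioid use.

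At trial level the size is unknown. The range of 2% to 44% of the planned difference, in either direction, multiplies three assumed quantities: a net placebo excess of 5 to 15 points, withdrawal at 12 to 48 hours, and an error of 1 to 3 NRS points. A reader might infer that the result is materially biased, or biased in favour of the drug. The documents support neither, because they give no rate, timing or imbalance. Confidence is medium for that reason.

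**What to change.** **Protocol 9.1, 10.3, 11.6.3 and 13.6** (with 11.6.1 and the Synopsis kept in line): separate leaving the rescue regimen from leaving data collection.

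- Record NRS-R and NRS-A at the time of withdrawal.
- In subjects who have not withdrawn consent and are still on site, continue scheduled scores and the recording of all analgesics to 72 hours, flagged as post-withdrawal.
- Reconcile these sections with 13.5 and 15.6.3.2, so that one rule says how long opioids are recorded.

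**SAP 7.6.2.1 and 7.6.2.2:** keep the planned primary analysis. Add a sensitivity analysis of the primary and opioid endpoints that uses the observed post-withdrawal data. For subjects already withdrawn without such data, use an alternative imputation, for example carried scores shifted over −3 to +3 NRS points within the 0 to 10 scale, with the projected opioid rate varied likewise. This fallback matters because the SAP reports that dose selection is complete and describes PCA data gaps in the past tense, so an amendment may come too late for some subjects. Report the number and timing of withdrawals for lack of efficacy by arm.

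**Cost:** amendment wording, a few bedside scores and one or two extra tables. The downside is that post-withdrawal scores reflect non-protocol analgesia and must be flagged and read as such. How pain is treated does not change.

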4. LIST OF ABBREVIATIONS AND DEFINITIONS OF TERMS

4.1. List of Abbreviations

AE	Adverse event
ANOVA	Analysis of variance
ANCOVA	Analysis of covariance
ASA	American Society of Anesthesiologists
AUC	Area under the curve
AUC _{0-tlast}	The area under the plasma concentration-time curve from the time of administration to the time of the last quantifiable concentration calculated using the lin/log trapezoidal rule
AUC _{0-∞}	The area under the plasma concentration-time curve from the time of administration extrapolated to infinity.
CFR	Code of Federal Regulations
CI	Confidence interval
C _{max}	The maximum observed plasma concentration obtained directly from the experimental data without interpolation
CRF	Case Report Form
ECG	Electrocardiogram
FDA	Food and Drug Administration
GCP	Good Clinical Practice
ICF	Informed consent form
ICH	International Conference on Harmonisation
IEC	Independent Ethics Committee
IRB	Institutional Review Board
MedDRA	Medical Dictionary for Regulatory Activities
NRS	Numeric rating scale
NRS-A	Numeric rating scale with activity
NRS-R	Numeric rating scale at rest
NSAIDs	Non-steroidal anti-inflammatory drugs
OBAS	Overall benefit of analgesia score
OR	Operating room

PCA	Patient-controlled analgesia
PK	Pharmacokinetic
PO	Oral
QTcB	The heart rate-corrected QT interval using Bazett's formula
QTcF	The heart rate-corrected QT interval using Fridericia's formula
SAE	Serious adverse event
SAP	Statistical analysis plan
SNRI	Selective norepinephrine reuptake inhibitors
SSRI	Selective serotonin reuptake inhibitors
λ_z	The apparent terminal elimination rate constant
$t_{1/2el}$	The apparent terminal elimination half-life
TEAE	Treatment-emergent adverse event
TKA	Total knee arthroplasty
T_{max}	The time to attain C_{max}
US	United States (of America)
wWOCF	windowed Worst-Observation-Carried-Forward

4.2. Definition of Terms

Pharmacokinetic terms are defined in [Section 12.4](#).

5. ETHICS

5.1. Institutional Review Board/Independent Ethics Committee

Prior to screening subjects into this study, the study site will obtain the approval of an Institutional Review Board (IRB)/Independent Ethics Committee (IEC) that complies with the International Conference on Harmonisation (ICH) Good Clinical Practice (GCP) and/or the United States (US) Food and Drug Administration (FDA) Title 21 Code of Federal Regulations (CFR) Part 56. Attention is directed to the basic elements that are required to be incorporated into the informed consent form (ICF) under 21 CFR Part 50.25 and ICH GCP.

5.2. Ethical Conduct of the Study

This study will be conducted in accordance with the clinical research guidelines established by the FDA Title 21 CFR, Parts 50, 54, 56, and 312, and the ICH GCP. Study documents will be maintained in accordance with applicable regulations.

5.3. Subject Information and Consent

Before a subject undergoes any study-specific screening procedures, the Investigator or designee will thoroughly explain to the subject the purpose of the study, the associated procedures, and any expected effects and potential adverse reactions. A copy of the IRB-approved ICF will be provided to the subject, who will be given sufficient time and opportunity to inquire about the details of the study and decide whether or not to participate. The subject, and the study staff with whom he/she discusses the ICF, will sign and date the ICF. A photocopy of the signed ICF will be given to the subject.

The Investigator will explain to the subject that he/she is completely free to decline entry into the study and may withdraw from the study at any time, for any reason, without risking her medical care. Similarly, the Investigator and/or Pacira Pharmaceuticals, Inc. (Pacira) will be free to withdraw the subject at any time for safety or administrative reasons. Any other requirements necessary for the protection of the human rights of the subject will also be explained, according to the current ICH GCP (E6) and the Declaration of Helsinki (1964, and as amended through 2000 [Edinburgh]).

